### 3. STUDY DESIGN

HPV-201 is a Phase 2, randomized, open-label efficacy study of VGX-3100 (DNA plasmids encoding E6 and E7 proteins of HPV types 16 and 18) administered by IM injection followed by EP delivered with CELLECTRA™ 2000 alone or in combination with imiquimod in adult women with histologically confirmed vulvar HSIL associated with HPV-16/18. Approximately 36 subjects will be enrolled. Twenty-four subjects will receive VGX-3100 alone and 12 subjects will receive VGX-3100 and topical imiquimod treatment. The Version 3.0 protocol amendment halts enrollment of the VGX-3100 with topical imiquimod study group. All subjects who have already been enrolled into the VGX-3100 with imiquimod study group will continue with all study visits per protocol, but no further participants will be enrolled into this group.

Subjects are randomized in a stratified manner according to (a) recurrent disease at screening (0 vs. 1 or more recurrences), (b) multifocal disease (1 vs. 2 or more lesions at screening), (c) Body Mass Index (BMI) category ( $\leq 25$  vs.  $>25$  kg/m^2) on Day 0, and (d) age category ( $<45$  years vs.  $\geq 45$  years) on Day 0.

To be eligible for the study, subjects must sign consent to participate and have a vulvar punch biopsy/biopsies of approximately 4 mm with lesion remaining, and photographs of the acetowhite vulvar lesion(s) at the time of screening. In the case of multifocal disease, the two lesions that potentially contain the most advanced disease, as judged by the Investigator, should be chosen for biopsy using vulvoscopy and documented using standardized high resolution photography with a digital single-lens reflex (SLR) camera on the case report form. Biopsy slides will be sent to a PAC for evaluation prior to enrollment. In order to be eligible for enrollment, the PAC must assign the diagnosis of vulvar HSIL based on the biopsy sample(s). Subjects must also have a vulvar specimen test positive for HPV genotype 16 and/or 18 to be eligible for participation in the study.

To assess quality of life and related impacts on subjects, PRO instruments will be provided and will include the Short Form Health Survey version 2 (SF-36v2™), the EQ-5D-5L (EuroQoL Research Foundation), WOMAN-PRO (WOMen with vulvar Neoplasia) Clinical Trial Version 2.0 and two additional PRO questions assessing quality of life after surgery or biopsy.

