In the event of worsening disease prior to the end of the study (i.e., Subgroup E), the subject will receive surgical treatment per the Investigator's judgment and will continue on study with vulvoscopy, but without further study treatment or biopsy. In the event of worsening disease at the final visit, the subject will receive standard of care treatment (not part of study activities) per their treating physician. If wide excision is conducted at or prior to the subjects last on site visit, the sample obtained will be sent to the PAC for evaluation. For a finding of carcinoma, subjects will receive surgical treatment, and be discontinued from study treatment. The event will be reported as an SAE per [section 7.1.4](#).

All visible lesions should be biopsied at Week 48. For subjects for whom Week 78 is their final visit, all visible lesions should be biopsied at Week 74. For subjects for whom the final visit is Week 96, all visible lesions should be biopsied at Week 96.

If there is a new lesion identified at evaluation, or a non-qualifying lesion that is rebiopsied and confirmed to be vulvar HSIL and HPV-16/18 positive at evaluation, a discussion will take place between the Medical Monitor and the Principal Investigator to determine if additional dosing at Week 52 is appropriate.

Pre-biopsy Vulvoscopy Finding	Minimally required procedure
No acetowhite lesion	Vulvar punch biopsy and lesion photography; biopsy should be conducted of the same qualifying lesion as study entry from the region of potentially most advanced disease based upon judgment of the Investigator; new lesions or lesions that did not qualify at baseline should be biopsied at evaluation.
Acetowhite Lesion	Vulvar punch biopsy and lesion photography; biopsy should be conducted of the same qualifying lesion as study entry from the region of potentially most advanced disease based upon judgment of the Investigator; new lesions or lesions that did not qualify at baseline should be biopsied at evaluation
Multiple acetowhite lesions	Vulvar punch biopsies and lesion photography; biopsy should be conducted of the same qualifying lesions as study entry from the region of potentially most advanced disease based upon judgment of the Investigator; new lesions or lesions that did not qualify at baseline should be biopsied at evaluation

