### 4.3.2 CRITERIA FOR WITHDRAWAL FROM THE STUDY

All subjects who begin treatment should be encouraged to complete all phases of the study, including those who discontinue treatment. A subject may voluntarily withdraw from study participation at any time. A subject may be withdrawn at any time at the discretion of the Investigator for any maternal obstetrical or medical complications after consultation with the medical monitor.

Subjects who become ineligible to continue on study based on no longer meeting exclusion criteria should be discontinued from study treatment, managed per routine standard of care and should continue on study without further biopsy.

Subjects who are withdrawn from study participation after starting treatment will not be replaced. Reasons for study withdrawal will be recorded in the electronic case report form (eCRF) and the subject's source document.

Should a subject fail to attend the clinic for a required study visit, the site should attempt to contact the subject and reschedule the missed visit as soon as possible. The site should also counsel the subject on the importance of maintaining the assigned visit schedule for follow-up and treatment of VIN, and ascertain whether or not the subject wishes to and/or should continue in the study based on previous noncompliance. In cases where the subject does not return for the rescheduled visit or cannot be reached to reschedule the missed visit, the site should make every effort to regain contact with the subject (3 telephone calls to the subject should be made and if that fails, then a certified letter is sent to the subject's last known mailing address) so that they can be considered withdrawn from the study for disposition purposes. These contact attempts should be documented in the subject's medical record. Should the subject continue to be unreachable, then and only then will she be considered to have withdrawn from the study with a primary reason of "Lost to Follow-up". For all other subjects withdrawing from the study, an alternative reason for discontinuation should be recorded in the eCRF.

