### 8.3 SAMPLE SIZE/POWER

A sample of 36 subjects will be randomized to receive either 6 mg VGX-3100 or 6 mg VGX-3100 plus imiquimod, IM followed by EP in a 2:1 ratio. This sample size provides 80% power to declare each study group superior to historical control with a one-sided

0.025 type 1 error level for each hypothesis, assuming the true proportion of subjects who achieve the primary endpoint is 20% and 28% for the respective treatment arms and 2% for the historical control, and that 90% are evaluable at Week 48 from randomization.

The Version 3.0 protocol amendment halts enrollment of the VGX-3100 with topical imiquimod study group. All subjects who have already been enrolled into the VGX-3100 with imiquimod study group will continue with all study visits per protocol, but no further participants will be enrolled into this group.

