#### **8.4 ANALYSES POPULATIONS**

Analysis populations will include:

- The modified intention to treat (mITT) population includes all subjects who receive at least one dose of Study Treatment and who have the analysis endpoint of interest. Subjects in this sample will be grouped to treatment arms as randomized. Analysis of the mITT population will be primary for the analysis of efficacy in this study.
- The per-protocol (PP) population comprises subjects who receive all doses of Study Treatments and have no protocol violations and who have the analysis endpoint of interest. Subjects in this sample will be grouped to treatment arms as randomized. Analyses on the PP population will be considered supportive of the corresponding mITT population for the analysis of efficacy. Subjects excluded from the PP population will be identified and documented prior to unblinding of the study database.
- The safety analysis set includes all subjects who receive at least one dose of Study Treatment. Subjects will be analyzed as to the treatment they received.

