## 8.9 EFFICACY ANALYSIS

The true treatment effect on the primary endpoint is  $p$ , where  $p$  denotes the true population probability of the primary endpoint for each arm. The primary hypothesis of superiority is:

$H_0: p \leq 0.02$  vs.  $H_1: p > 0.02$ , for each treatment study group separately.

A p-value for these hypothesis tests and corresponding 95% confidence intervals will be computed based on the exact method of Clopper-Pearson. Superiority will be concluded if the one-sided p-value is  $< 0.025$  and the corresponding lower bound of the 95% CI exceeds 0.02.

The secondary efficacy binary endpoints will be analyzed in the same manner as the primary hypothesis, but without the hypothesis test p-values. All of the efficacy binary endpoints will be analyzed in two ways: a) based on qualifying and new lesions, and b) based on all lesions. Also, the Week 74 binary endpoint will be analyzed overall, and according to four or five doses received, and the Week 96 binary endpoint will be analyzed overall, and according to four, five, or six doses received.

For the analyses, the efficacy time frame is defined by any time starting from 14 days prior to the -specified visit week.

The anatomic extent endpoint will be analyzed by calculating the mean percent change and associated 95% t-distribution based confidence interval. The percentage of subjects with no clinically significant lesion resolution (reduction in lesion size of 25% or less), partial lesion resolution (26-99% reduction), and complete reduction (100% reduction) will be summarized with point estimates and associated exact Clopper-Pearson 95% confidence intervals.

An exploratory analysis will examine clearance outside of the vulva. This will be analyzed in the same manner as vulvar clearance.

An exploratory analysis will examine the relationship between the primary efficacy endpoint and a) miRNA results, b) vulvoscopy results, and c) HPV results. Relationships will be examined with contingency tables and/or logistic regression models which model the primary endpoint versus these results and treatment group as regressor variables.

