### **8.13 MISSING VALUES**

Missing data will not be imputed or replaced, and calculations will be done on reported values.

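### No planned efficacy analysis covers all treated women: the primary set keeps only those with a Week 48 result, which probably overstates the response rate slightly

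*Protocol*

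**What the plan says.** All references are to Version 5.0 of the protocol.

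- **Primary set (8.4).** The modified intention-to-treat population "includes all subjects who receive at least one dose of Study Treatment and who have the analysis endpoint of interest". Its analysis is named as primary for efficacy. The per-protocol set, which is supportive, also requires the endpoint to be present.
- **Missing data (8.13).** "Missing data will not be imputed or replaced, and calculations will be done on reported values".
- **Endpoint (8.1, 8.9).** The primary endpoint rests on tissue collected at Week 48. The efficacy window opens 14 days before the visit week.
- **Responder rule (3.2.1, Table 3).** A woman who received non-study treatment for vulvar HSIL is a non-responder. So is any woman with histologically confirmed progression to carcinoma.
- **Women who become ineligible (4.3.2).** They stop study treatment and are "managed per routine standard of care and should continue on study without further biopsy". Women withdrawn after starting treatment are not replaced.
- **Women who worsen (3.2).** They receive surgery at the Investigator's judgment and "will continue on study with vulvoscopy, but without further study treatment or biopsy".
- **Sample size (8.3).** "A sample of 36 subjects will be randomized" in a 2:1 ratio, with 90% expected to be evaluable at Week 48.

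**The concern.** The hypothesis in section 2 concerns the percentage of treated women who respond. The planned estimate is the percentage among those still sampled at Week 48. If treated women without a result are mainly failures, the estimate is too high. In a comparison of two arms, similar losses on both sides could partly cancel. Here each arm is compared with a constant, so nothing offsets the selection.

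There is also a gap in the wording. Table 3 can class a woman as a non-responder from the treatment she received, without any Week 48 tissue. Sections 8.1 and 8.4 do not say whether such a woman counts as having the endpoint. An analyst could leave her out and still comply with 8.4, which would remove a known failure from the denominator.

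What is at stake is mainly the accuracy of the reported response rate. The steps below also check whether the superiority conclusion is at risk.

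**Working it through.** **Inputs.**
- Arm sizes, section 3: "Twenty-four subjects will receive VGX-3100 alone and 12 subjects will receive VGX-3100 and topical imiquimod treatment".
- Error level, 8.3: one-sided, "0.025 type 1 error level for each hypothesis".
- Response rates, 8.3: 20% and 28%, against a historical 2%.
- Evaluable share, 8.3: 90%.
- Test, 8.9: exact binomial with Clopper-Pearson limits. "Superiority will be concluded if the one-sided p-value is" below 0.025 and the lower 95% limit exceeds 0.02.
- Spontaneous regression, 1.1.3: 1.5% to 5%.

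**Step 1: reproduce the plan's sample size.** Success requires the smallest count x for which P(X ≥ x | n, 0.02) < 0.025. That count is 2 for any n from 2 to 12, and 3 for any n from 13 to 25.
- At 20%, n = 20 gives power 79.4% and n = 21 gives 82.1%, so 21 evaluable women are needed. 21 / 0.9 = 23.3, rounded up to 24.
- At 28%, n = 9 gives 76.6% and n = 10 gives 81.7%, so 10 are needed. 10 / 0.9 = 11.1, rounded up to 12.
- 24 + 12 = 36, which matches the protocol. The calculation applies the 20% and 28% to evaluable women.

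**Step 2: largest overstatement at the planned 10% missing.** If every missing woman is a non-responder, the all-treated rate equals the evaluable rate times 0.9.
- 0.20 × 0.9 = 0.180, a difference of 2.0 points.
- 0.28 × 0.9 = 0.252, a difference of 2.8 points.
- In relative terms, 1 / 0.9 = 1.11, or 11% in each arm.

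As an example, 3 responders among 22 evaluable women give 13.6% (95% CI 2.9 to 34.9). The same 3 among 24 treated women give 12.5% (2.7 to 32.4). Both lower limits exceed 2%.

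**Step 3: effect on the decision.** With 24 treated, the threshold stays at 3 for any evaluable number from 13 to 24. With 12 treated, it stays at 2 for any evaluable number from 2 to 12. Adding the missing women back as non-responders leaves the responder count unchanged, so the decision does not change over those ranges.

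As a check on type I error, take a true all-treated rate of 2% with only non-responders missing. In the 24-woman arm the error of the current rule is 0.0118 at 0% and at 10% missing, and 0.0119 at 20% (assumed). In the 12-woman arm it is 0.0231 at all three. All are below 0.025.

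**Step 4: power if missing counts as non-response.**
- P(X ≥ 3 | 24, 0.18) = 83.3%.
- P(X ≥ 2 | 12, 0.252) = 84.5%.

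Complete-case power, averaged over a binomial number evaluable with share 0.9, is also 83.3% and 84.5%. The two agree because the thresholds are constant over the likely denominators. At 20% missing, which is an assumption, the all-treated analysis has 76.3% and 78.7%.

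**The case against.** **The biopsy stop for worsening disease.** A reader might infer that the protocol removes worsening women from the primary analysis by ending their biopsies. The documents do not support that as the main route. The same sentence of 3.2 sends these women for surgery at the Investigator's judgment. Once given non-study treatment they are Table 3 non-responders, as are confirmed carcinomas. Post-baseline lesion area is quantified only from Week 48 onward, so worsening is mostly identified at or after the primary biopsy. An unscheduled biopsy showing only HSIL allows scheduled visits to continue (Table 12). The stop therefore bears mainly on the exploratory Week 74 and 96 endpoints. What survives is the woman who worsens early and is not operated on, and the unstated link between Table 3 and 8.4.

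**Direction and size.** A reader might also infer that upward bias is established, or that it threatens the superiority claim. Direction depends on who is missing, which the protocol cannot show. A woman who stopped early still had at least one dose and could have responded. The size is small and the decision at the planned arm sizes is unaffected.

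**Other mitigations.** The window in 8.9 states no upper limit and 4.3.2 asks sites to reschedule missed visits, so a late biopsy need not be lost. Women who become ineligible may well be treated for HSIL and so become non-responders. Section 8.5 reports disposition and the size of each population, so a reader could approximate the all-treated rate. These points reduce the problem without removing it, because the protocol itself expects 10% to be non-evaluable.

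**The analysis plan.** A separate plan, not at hand, could add sensitivity analyses. The choice of primary set and the blanket rule in 8.13 are nevertheless fixed in the protocol.

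**Conclusion.** The point holds in a limited form. Sections 8.4 and 8.13 together fix a complete-case primary analysis, and the only other efficacy set carries the same condition. Treated women lost or unsampled before Week 48 therefore appear in no planned response rate. With spontaneous regression at 1.5% to 5%, upward bias is the likely direction, though it is not demonstrated.

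The ceiling of 2.0 and 2.8 points rests on three things: 10% missing, every missing woman a non-responder, and the protocol's 20% and 28% read as rates among evaluable women.

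The finding that the decision is unaffected applies to arms of 24 and 12. Final arm sizes after imiquimod enrolment was halted are not given. If the VGX-3100-alone arm grew (an assumption), the threshold rises from 3 to 4 between n = 31 (3 responders, p = 0.0237) and n = 32 (p = 0.0258). The choice of denominator could then matter.

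This should be corrected, but it does not undermine the trial's main conclusion at the planned sizes.

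**What to change.** 1. In 8.4, make the primary efficacy population all dosed subjects, grouped as randomised, with a missing Week 48 histology or HPV result counted as non-response.
2. In 8.1 or 8.4, state that a woman classed as a non-responder under Table 3 counts as such whether or not Week 48 tissue exists.
3. Keep the current modified intention-to-treat set as a sensitivity analysis.
4. Amend 8.13 so that its no-imputation rule does not apply to the binary efficacy endpoints.

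The cost is a change of wording and a slightly lower reported rate. At the planned 10% missing, the thresholds stay at 3 of 24 and 2 of 12. Power stays above the stated 80%. If 20% were missing, power would fall just below 80% in both arms. No study procedure or clinical rule needs to change.

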#### **8.5 SUBJECT DISPOSITION**

Disposition will be summarized by treatment for all randomized subjects and will include the number and percentage randomized, the number and percentage who received each dose and the number who completed the trial. The number and percentage of subjects who discontinued will be summarized overall and by reason. The number in each analysis population will also be presented.

#### **8.6 DEMOGRAPHIC AND OTHER BASELINE CHARACTERISTICS**

Demographic and baseline data will be summarized with descriptive statistics: mean standard deviation, minimum, median, and maximum values for continuous variables, and percentages for categorical variables, by treatment arm, for the mITT population. Prior and concomitant medications will also be summarized with percentages in this fashion.

#### **8.7 MEDICAL HISTORY**

The percentage of subjects with abnormal medical history findings will be summarized by body system, by treatment arm, for the mITT population.

## 8.8 PRIOR AND CONCOMITANT MEDICATIONS

Prior medications are considered those medications taken prior to the first dose of study drug (i.e., Day 0). Concomitant medications are those used on or after Day 0. Partial start dates of prior and concomitant medications will be assumed to be the earliest possible date consistent with the partial date. Partial stop dates of prior and concomitant medications will be assumed to be the latest possible date consistent with the partial date. Data for all prior and concomitant medications will be summarized with percentages by treatment arm, for the mITT population.

## 8.9 EFFICACY ANALYSIS

The true treatment effect on the primary endpoint is  $p$ , where  $p$  denotes the true population probability of the primary endpoint for each arm. The primary hypothesis of superiority is:

$H_0: p \leq 0.02$  vs.  $H_1: p > 0.02$ , for each treatment study group separately.

A p-value for these hypothesis tests and corresponding 95% confidence intervals will be computed based on the exact method of Clopper-Pearson. Superiority will be concluded if the one-sided p-value is  $< 0.025$  and the corresponding lower bound of the 95% CI exceeds 0.02.

The secondary efficacy binary endpoints will be analyzed in the same manner as the primary hypothesis, but without the hypothesis test p-values. All of the efficacy binary endpoints will be analyzed in two ways: a) based on qualifying and new lesions, and b) based on all lesions. Also, the Week 74 binary endpoint will be analyzed overall, and according to four or five doses received, and the Week 96 binary endpoint will be analyzed overall, and according to four, five, or six doses received.

For the analyses, the efficacy time frame is defined by any time starting from 14 days prior to the -specified visit week.

The anatomic extent endpoint will be analyzed by calculating the mean percent change and associated 95% t-distribution based confidence interval. The percentage of subjects with no clinically significant lesion resolution (reduction in lesion size of 25% or less), partial lesion resolution (26-99% reduction), and complete reduction (100% reduction) will be summarized with point estimates and associated exact Clopper-Pearson 95% confidence intervals.

An exploratory analysis will examine clearance outside of the vulva. This will be analyzed in the same manner as vulvar clearance.

An exploratory analysis will examine the relationship between the primary efficacy endpoint and a) miRNA results, b) vulvoscopy results, and c) HPV results. Relationships will be examined with contingency tables and/or logistic regression models which model the primary endpoint versus these results and treatment group as regressor variables.

